## 3.3.2 Inclusion criteria

- 1. Diagnosis of relapsed or refractory chronic lymphocytic leukaemia (according to the definition of the IWCLL (R10-4429))
- 2. Previous therapy of CLL with at least two prior treatment regimens
- 3. At least one of the following criteria for active disease as defined by the IWCLL
  - (1) Evidence of progressive marrow failure as manifested by the development or worsening of anemia and/or thrombocytopenia
  - (2) Massive (i.e. at least 6 cm below the left costal margin) or progressive or symptomatic splenomegaly as assessed by the investigator;
  - (3) Massive nodes (i.e. at least 10 cm in longest diameter) or progressive or symptomatic lymphadenopathy as assessed by the investigator

- (4) Progressive lymphocytosis with an increase of more than 50% over a 2-month period or a lymphocyte doubling time of less than 6 months
- (5) Constitutional symptoms, defined as any one or more of the following disease-related symptoms or signs:
  - Unintentional weight loss of 10% or more within the previous 6 months
  - Fevers higher than 38.0°C for 2 or more weeks without other evidence of infection
  - Night sweats for more than 1 month without evidence of infection
- 4. Absolute lymphocyte count lower than  $200 \times 10^9$ /l
- 5. ECOG Performance Status 0, 1 or 2
- 6. Age  $\geq$  18 years.
- 7. Written informed consent which is consistent with ICH-GCP guidelines and local legislation

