## 3.3.3 Exclusion criteria

- 1. Prior treatment with anti CD 20 therapy within 4 weeks, or alemtuzumab within 8 weeks, or any **cytotoxic** antileukemia therapy within 2 weeks, **Ibrutinib or Idelalisib within 1** week prior to the first administration of the trial drug
- 2. Prior allogeneic stem cell transplantation
- 3. Active autoimmune haemolytic anemia
- 4. Active autoimmune thrombocytopenia
- 5. Known transformation to an aggressive B-cell malignancy (e.g. large B-cell lymphoma, Richter's syndrome)
- 6. Concurrent treatment with systemic glucocorticosteroids at doses equivalent to prednisolone 20 mg/d or higher.
- 7. Prior history of malignancy other than CLL (except basal cell or squamous cell carcinoma of the skin, or carcinoma in situ of the uterine cervix or breast treated with curative therapy) unless the subject has been free of disease and without treatment for at least 5 years.
- 8. AST, and/or ALT > 2.5 x upper limit of normal (CTCAE grade 2 or higher)
- 9. Total bilirubin > 1.5 x upper limit of normal (CTCAE grade 2 or higher)
- 10. ANC  $< 1.0 \times 10^9$ /L (without growth factor support).
- 11. Platelets  $< 25 \times 10^9$ /L (without growth factor support or transfusions)
- 12. Estimated GFR <45 mL/min (see Section 10.3)
- 13. Proteinuria CTCAE grade 2 or higher
- 14. Significant concurrent medical disease or condition which according to the investigator's judgement would either compromise patient safety or interfere with the evaluation of the safety of the test drug.
- 15. Any infectious disease requiring treatment at the time of enrolment or within the previous 2 weeks.
- 16. Active Hepatitis B or Hepatitis C, or laboratory evidence for a chronic infection.
- 17. HIV infection
- 18. CMV viremia
- 19. Women of childbearing potential not using a highly effective method of birth control during the trial until one year after the last dose. Highly effective methods of birth control are defined as those which result in a low failure rate (i.e. less than 1% per year) when

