5.4.5.2 Laboratory values of special interest

Neutropenia, thrombocytopenia and leukopenia

Episodes of low neutrophil, platelets and WBC counts are of special interest. Episodes with CTCAE grade 3 and 4 and CTCAE grade 4 lasting 7 or more days will be analyzed.

An episode of e.g. low neutrophils starts with the first occurrence of a CTCAE grade ≥ 3 and lasts until the first time the CTCAE grade falls back to ≤ 2 .

In case the episode starts during EOT or Follow-up, the duration of this episode is defined to be missing. The reason for this approach is that after EOT laboratory data is only captured infrequently and therefore the duration of an episode would be overestimated due to lack of data.

If the episode starts before EOT and the CTCAE grade of the respective parameter does not fall back to grade ≤ 2 and the patient dies, the end of the episode is defined by the date of death. If the episode starts before EOT and lasts during Follow-up the episode is censored with the date of DBL.

Hepatic enzyme elevations (potential Hy's law cases)

Special attention will be paid to patients fulfilling the criteria for potential Hy's law cases. These are defined as those cases where a combination of all of the following events occurred: any on-treatment value of ALT and/or AST > 3 times upper limit of normal (3 x ULN) with total bilirubin \ge 2 x ULN and ALKP < 2 x ULN. The events can occur in any order, but must occur within 14 days of the previous event, i.e. the second event must occur within 14 days of the first event, and the third event must occur within 14 days of the second event.

Possible clinically significant abnormal lab values

Possible clinical significance based on CTCAE grading is defined as CTCAE grade 2 or higher with an increase of at least one CTCAE grade from baseline, please refer to Section
9.2. for further details. If the baseline value is missing, all post-baseline values with CTCAE

grade 2 or higher will be classified as possibly clinically significant. For the laboratory parameters recorded that do not have a CTCAE grading defined, the BI default rules for clinical significance should be applied (5).

Tumour lysis syndrome (TLS)

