6. GENERAL ANALYSIS DEFINITIONS

6.1 TREATMENTS

In this Phase I trial, treatments are not randomised (open-label, dose escalation). Different dose levels of BI 836826 are being administered. The data will be presented for all dose cohorts separately and in total over all dose cohorts. To justify the MTD determination, DLTs occurring during the MTD evaluation period (during the first treatment course) will be presented separately from those occurring during the complete on-treatment period.

"Analysing treatment" will be used for reporting of treatment emergent adverse events (AE) and to differentiate between screening, on-treatment, post-treatment and post-study safety data. The inequalities start date \leq onset date of AE < end date will determine whether the AE will be assigned to the "analysing treatment" or not. Table 6.1:1 defines the "analysing treatment period" which will be used for reporting of treatment emergent AEs and safety laboratory parameters. Safety data recorded during the Residual Effect Period (REP) will be considered as on-treatment.

If not specified otherwise, all safety tables will be based on the on-treatment period. AEs that have an onset date during the screening or post-study periods will be displayed in separate listings from those occurred during the on-treatment period.

T 11 (1	1 D C '.'	C 1 .		. 1()
Table 6 1:	I Definition	of analysing	treatment	neriodist
I dolo o.i.	1 Dominion	OI unui yonii 🗲	, u cuuniciit	periodisi

Analysing treatment period	Start date (including)	Stop date (excluding)	
Screening	Date of informed consent	Date of first administration of study medication	
On-treatment	Date of first administration of study medication	Start date of 'Follow-up'	
Follow-up	Date of end of REP +1	Start date of 'Post-study'	
Post-study	Last date patient status obtained / last date patient known to be alive + 1 (if patient is lost to follow-up) / date of refusal + 1 day / the date patient died + 1	During the trial: open / empty; after database lock (DBL): DBL + 1 day	

The initial study medication assigned at the beginning of the first treatment course will be used as the label of the analysing treatment.

The actual dose of study medication administered on the day each AE started will also be derived. This will be presented in patient listings, but will not be used for defining treatments for analysis.

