6.7 BASELINE, TIME WINDOWS AND CALCULATED VISITS

Study days and visits will be labelled according to the flow chart of the CTP.

Unless otherwise specified, baseline is defined as the time-point closest to but prior to first administration of study medication. If no time is specified and the date is the same as the first administration date, then it will still be considered baseline if not specified otherwise.

Laboratory values: Baseline is defined as the latest time-point before start of the very first administration of study medication. For laboratories where not only the examination date but also time are recorded, examination time has to be taken into account when defining baseline. That is, a laboratory value on the same date as the first study drug administration is considered as baseline value if and only if the time of laboratory value is before or the same as the time of the start of first study drug administration.

If any of these times are missing (either no time of start of first study drug administration or no lab sample stating that it was taken prior to start of first study drug administration) and so it cannot be concluded whether the blood sampling was done before or at the same time of the start of first study drug administration, the last available laboratory assessment before first study drug administration will be taken (Screening laboratory).

For graphical presentations of laboratory data, baseline will be coded as Day = 1.

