7.8.2 Laboratory data

The analyses of laboratory data will be descriptive in nature and will follow the standard procedure laid down in the SOP_"Display and Analysis of Laboratory Data" (5). Patients will be counted under the initial treatment. The analysis of laboratory data will use the same 'analysing treatments' as described for the AEs, except for that the baseline laboratory value (as defined in Section 6.7) will be included in the 'on treatment' period. Patients having at least one post-baseline laboratory value will be displayed in the descriptive analyses. Patients with missing CTCAE grade at baseline or no baseline value but with post-baseline laboratory values will be displayed in the category "Missing CTCAE grade at baseline"

Single time courses by initial treatment will be used to display converted laboratory values over time by dose cohort. The graphs may be truncated if sufficient data is not available. These graphs will be displayed in Chapter 16.1.9.2 for the following parameters.

Haematology: haemoglobin, WBC count and platelets

Differentials: neutrophils (absolute count), absolute lymphocyte count, and natural killer (NK) cells

Enzymes: LDH

Clinically relevant abnormalities (as defined in Section 5.4.5.1) will also be summarised.

Descriptive statistics, including change from baseline, frequency of patients with transitions relative to the references range, will be provided. No post-study laboratory values will be considered. CTCAE grade for applicable laboratory parameters will be calculated according to CTCAE v4.0. The following outputs will be presented:

- Baseline, last value and difference from baseline
- Worst CTCAE grade experienced during the on-treatment period
- Transitions of the CTCAE grade from baseline to the worst lab values, from baseline to the last lab values, and from the worst to last values during the on-treatment period
- Possible clinically significant laboratory values

Note: For calculating the change in CTCAE grade from baseline, patients with a CTCAE grade of -9 (no CTCAE grade defined) will be treated as a CTCAE grade 0 for all analyses. In laboratory listings, the CTCAE grade is displayed as -9.

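### SAP 7.8.2 counts the pre-dose baseline laboratory value as on-treatment, so the worst on-treatment grade can be one recorded before any drug was given

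*SAP*

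**What the plan says.** SAP 7.8.2 gives laboratory data the same analysis periods as adverse events, "except for that the baseline laboratory value (as defined in Section 6.7) will be included in the 'on treatment' period". SAP 6.7 fixes what that value is: "Baseline is defined as the latest time-point before start of the very first administration of study medication". If clock times are missing, the value falls back to the screening laboratory, which under Protocol 6.2.1 can be up to 14 days old.

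SAP 7.8.2 then lists its outputs. One is "Worst CTCAE grade experienced during the on-treatment period". Another is a set of grade transitions: baseline to worst, baseline to last, and worst to last. Neither item says that the worst value must come from a sample taken after dosing. The section does state "Patients having at least one post-baseline laboratory value will be displayed in the descriptive analyses", but that decides which patients appear, not which values feed the worst grade.

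For cytopenia episodes, SAP 5.4.5.2 says: "An episode of e.g. low neutrophils starts with the first occurrence of a CTCAE grade" of 3 or more. An episode ends when the grade returns to 2 or lower. Episodes are defined for neutrophils, platelets and white cells.

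The entry criteria allow low counts at baseline. One route to showing active disease (Protocol 3.3.2) is "Evidence of progressive marrow failure as manifested by the development or worsening of anemia and/or thrombocytopenia". Protocol 3.3.3 excludes platelets only below 25 x 10^9/L ("without growth factor support or transfusions") and neutrophils below 1.0 x 10^9/L. The criteria shown set no lower limit for haemoglobin or white cells.

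**The concern.** A table headed on-treatment should describe what was seen once treatment had started. With baseline inside the window, the worst grade can never be better than the baseline grade, so a patient who only improves carries the pre-treatment abnormality into the on-treatment table.

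The patients exposed to this are those the plan elsewhere hopes to see. SAP 5.2.2 counts improved haemoglobin, platelets and neutrophils as secondary efficacy endpoints. One patient could be an improver in the efficacy table and appear at the unimproved grade in the on-treatment safety table.

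The tables are shown by dose cohort, and the escalation cohorts hold one, three or six patients (Protocol 7.6). One reclassified patient moves a cohort's percentage by 1/6 = 17, 1/3 = 33 or 1/1 = 100 points.

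**Working it through.** The plan gives no figure to reproduce here. The check compares the worst grade with and without the baseline value.

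**Rule.** Literal SAP: worst = max(baseline grade, all later on-treatment grades). Alternative: worst = max(later on-treatment grades). The two differ only if every later grade is strictly better than baseline.

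**Illustration with platelets (x 10^9/L).** The documents do not print CTCAE cut-offs. I assume grade 4 below 25, grade 3 below 50, grade 2 below 75, and grade 1 below a lower limit of normal of 150. Baseline is 40 (grade 3) in each case.

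| Patient | Later values | Later grades | Worst, baseline included | Worst, later samples only |
|---|---|---|---|---|
| Recovers | 60, 65, 70, 80, 90 | 2, 2, 2, 1, 1 | 3 | 2 |
| Persists | 45, 38, 60, 70 | 3, 3, 2, 2 | 3 | 3 |
| Worsens | 60, 22, 40, 55 | 2, 4, 3, 2 | 4 | 4 |

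Only the recovering patient changes. For that patient:

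- Baseline to worst reads 3 to 3 with baseline included, and 3 to 2 without it.
- Worst to last reads 3 to 1 with baseline included, which looks like recovery from an on-treatment grade 3. Without it the entry is 2 to 1.
- Baseline to last reads 3 to 1 either way.
- Every later value is at least 40 x 1.5 = 60, the 50% rise that SAP 5.2.2 requires for platelet improvement, if enough of the samples fall at qualifying response assessments.

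**Episodes.** If the baseline sample counts, the recovering patient has an on-treatment grade 3 platelet episode that starts before the drug. If only later samples count, there is none. The persisting patient has an episode either way, but nothing marks it as already present. Protocol 6.2.2.1 schedules a safety sample before dosing on day 1 and Protocol 6.2.2.2 another on day 2, so starting the episode at baseline usually adds about one day. It adds more only when baseline falls back to a screening sample. For neutrophils the entry limit of 1.0 x 10^9/L leaves little room, if grade 3 starts below that value (assumed): the count would have to fall between the screening check and the day 1 sample.

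**How often.** The documents do not allow a count. As a yardstick only, suppose there is no drug effect and a patient's k + 1 values are exchangeable. The chance that baseline is the single worst value is then at most 1/(k + 1):

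- course 1 only (days 2, 3, 4, 8): k = 4, 1/5 = 20%;
- four courses plus the EOT visit: k = 4 + 3 x 4 + 1 = 17, 1/18 = 5.6%;
- eight courses plus the EOT visit: k = 4 + 7 x 4 + 1 = 33, 1/34 = 2.9%.

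The chance that baseline has a strictly worse grade is no larger. A drug that lowers counts would reduce these shares, and improvement on treatment would raise them.

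**The case against.** Five points can be made for the plan as written.

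1. **Other outputs separate old from new.** SAP 5.4.5.2 calls a value possibly clinically significant only if it is grade 2 or higher and at least one grade above baseline, so the recovering patient is not flagged there. Baseline-to-last transitions show improvement. This stands and lowers the weight of the point, but it does not correct the worst-grade, baseline-to-worst or worst-to-last outputs.
2. **The laboratory SOP may restrict worst values to post-baseline samples.** SAP 7.8.2 cites an SOP that is not among the documents. That is possible, but the SAP text makes an explicit exception the other way, and a reader of the SAP has only that.
3. **Most pre-existing cytopenia would be reported anyway.** This is correct. A low count that persists in even one later sample enters the worst-grade table with or without baseline, because that output has no treatment-emergent filter.
4. **The size is easily overstated.** A reader might multiply an assumed share of patients entering at grade 3 by the planned sample size and call the product misreported patients. The documents give no such share, and the product would count everyone exposed to the rule, not those whose result changes.
5. **Dose decisions do not rest on this table.** A reader might infer that the MTD or the dose for further development is distorted. Protocol 5.2.1.1 bases DLT and MTD on adverse events in course 1, and ties haematological adverse events, not laboratory grade tables, to the later dose. The adverse event period in SAP 6.1 starts at first administration, and the baseline exception is confined to laboratory data. That inference is not supported.

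**Conclusion.** The point holds in a limited form. Followed literally, SAP 7.8.2 reports a pre-dose grade as the worst on-treatment grade for any patient whose later grades are all better. It also removes improvement from the baseline-to-worst transitions and can create an apparent recovery in the worst-to-last transitions. Platelet and white cell episodes that began before treatment can be counted as on-treatment without a flag; the neutrophil case is narrow and the added duration is usually small.

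The number of patients is unknown. The percentages above rest on exchangeable values and no drug effect and are not estimates for this trial. The platelet example rests on assumed grade cut-offs, but the logic does not depend on them. The primary endpoint and the adverse event tables are unaffected. This is a defect of definition in secondary, descriptive safety outputs, worth correcting because the correction is so small.

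**What to change.** In SAP 7.8.2:

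- Keep the baseline value only as the reference for change from baseline and for transitions.
- Derive worst value and worst grade, including the worst side of both transition tables, from on-treatment samples taken after the start of the first infusion.
- Flag any episode under SAP 5.4.5.2 that is already at grade 3 or higher at baseline, and show flagged and new episodes separately.

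The filter must use date and time. Table 6.1:1 opens the on-treatment period on the date of first administration, so deleting the exception alone would still let in a day 1 pre-dose sample. The SAP should also say how a day 1 sample without a clock time is classed.

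The cost is a line or two of text, a date-time condition and one flag variable; no new data are needed. The change will not remove baseline cytopenias that persist after dosing, which must still be read against the baseline grade.

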#### 5.2.3 Assessment of safety laboratory parameters

5.2.3.1 General safety laboratory parameters

Blood samples and urine have to be collected at the time points specified in the Flow Chart. Blood samples should be collected more frequently in case of relevant toxicities; e.g. in case of grade 4 neutropenia or thrombocytopenia, to document as accurately as possible the duration of the AE. Safety laboratory examinations will include haematology, biochemistry, coagulation and qualitative urine analysis:

Haematology	Haemoglobin, red blood cell count (RBC), white blood cell count (WBC) with differential, platelets (PLT)
	Reticulocytes have to be measured only at Screening, Visit 1, Day 1 of each treatment course, at the EOT visit and during follow-up.
Biochemistry	Glucose, sodium, potassium, calcium, inorganic phosphate, creatinine, aspartate amino transferase (AST), alanine amino transferase (ALT), alkaline phosphatase (AP), lactate dehydrogenase (LDH), total bilirubin (if elevated provide direct bilirubin), urea, total protein, albumin, uric acid
	Serum immunoglobulin levels (IgG, IgM, IgA), direct antiglobulin test have to be measured only at Screening, Visit 1, Day 1 of each treatment course, at the EOT visit and during follow-up.
Coagulation	Activated partial thromboplastin time (aPTT), prothrombin time (PT), international normalised ratio (INR) where indicated (e.g. treatment with vitamin K antagonists)
Urine	pH, glucose, erythrocytes, leukocytes, protein, nitrite will be analysed by dipstick and reported as semiquantitative measurements. In case of pathological findings, further evaluation should be performed and results documented.
Pregnancy test	A serum pregnancy test needs to be obtained at the time points indicated in the Flow Chart in patients of childbearing potential.

In case a treatment course is delayed due to an adverse event, the patient should visit the site at least once a week for assessment of safety laboratory and adverse events. More frequent visits may be appropriate as assessed by the investigator.

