**Trial Protocol** 

[figure not shown]
Page 110 of 111

	(DLT)	
	Change 5: Section 5.2.3.1: General safety laboratory parameters	
Description of change	Change 1: Deletion of visit window: Course 1, Day 8	
	Change 2: Exclusion criterion 1 was changed from "or any other antileukemia therapy within 2 weeks," to "or any cytotoxic antileukemia therapy within 2 weeks, Ibrutinib or Idelalisib within 1 week" The restrictions section was changed from: "Prior antileukemia therapy must have been discontinued at least two weeks before the first administration of the trial drug" to "Prior antileukemia therapy must have been discontinued in line with the requirements per exclusion criterion 1"	
	Change 3: Sub-section 3.3.4.2.1 was added describing Trial stopping rules	
	Change 4: The following was added: "The additional following haematologic adverse events will be considered DLT:	
	• Grade 4 neutropenia lasting more than 7 days.	
	
 
Febrile neutropenia not resolving within 48 hrs with appropriate treatment (antibiotics, antivirals, antifungals, growth factor support)
 
Grade 4 thrombocytopenia lasting more than 7 days, or grade 3-4 thrombocytopenia with clinically significant bleeding
 
Grade 4 anemia" The following was deleted: "Complications resulting from haematological adverse events, e.g. bleeding due to thrombocytopenia or infection due to neutropenia are classified as non haematological adverse events and are covered
 
	

Page 111 of 111

	Change 5: "Blood samples should be collected more frequently in case of relevant toxicities; e.g. in case of grade 4 neutropenia or thrombocytopenia, to document as accurately as possible the duration of the AE." was added.
--	---

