Rationale for change         Image: Image of the second s	
 
Change 1: To ensure that all patients can be assessed for duration of neutropenia and thrombocytopenia on the same day during the MTD evaluation period
 
Change 2: Ibrutinib and Idelalisib were recently approved in the countries in which the trial is recruiting patients. Both drugs have a short half live and should be eliminated after 7 days after the last dose, therefore not posing additional risks for interaction with trial medication. Patients should not receive the first dose of BI 836826 earlier than 1 week after the last dose of Ibrutinib or Idelalisib to ensure elimination prior to starting BI 836826, while also allowing expeditious access to the investigational treatment for patients in need of treatment options.
 
Change 3: Trial stopping rules were described in more details according to FDA recommendations
 
Change 4: The DLT definition was refined to include specific haematologic adverse events according to FDA recommendations
 
Change 5: More frequent measurements in case of relevant findings, e.g. to quantify the duration of Grade 4 neutropenia and/or thrombocytopenia
 

---	---

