5. ENDPOINTS

5.1 PRIMARY ENDPOINTS

The primary objective of this study is the tolerability and safety of BI836826 as reflected by the MTD. Thus, primary endpoints of this trial are the MTD and the number of patients with DLTs during the MTD evaluation period. Instead of the MTD, an optimal biological dose (OBD) might be defined instead.

Maximum tolerated dose (MTD):

The MTD is defined as the highest dose studied for which the incidence of DLT is no more than 17% (i.e., 1/6 patients) during the MTD evaluation period.

The MTD evaluation period is defined as the duration of the first treatment course (i.e. 14 days after first administration of BI 836826).

For the definition of DLT please refer to the CTP Section 5.2.1.1. Please note that the definition of DLT was changed during the trial by amendments of the CTP. With CTP version 6 (04 March 2015), the following additional haematologic AEs were considered DLT:

- Grade 4 neutropenia lasting more than 7 days
- Febrile neutropenia not resolving within 48 hrs with appropriate treatment (antibiotics, antivirals, antifungals, growth factor support)
- Grade 4 thrombocytopenia lasting more than 7 days, or grade 3-4 thrombocytopenia with clinically significant bleeding
- Grade 4 anemia

The respective definition of DLT included in the CTP effective at the start time of the Adverse Event (AE) qualifying for a DLT was used.

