7. PLANNED ANALYSIS

For End-Of-Text tables, the set of summary statistics is: N / Mean / standard deviation [StD] / Min / Median / Max. Efficacy data are presented by dose cohort. Displays of safety data will be presented by dose cohort and in total.

For tables that are provided for endpoints with some extreme data, median, quartiles and percentiles should be preferred to mean, StD, min and max.

For time-to-event analysis tables, the set of statistics is: number of patients [N(%)], Number of patients with event [N(%)], <Time to event> [months] followed by P25 (25th percentile), median, P75 (75th percentile), Number of patients censored [N(%)]. If not specified otherwise, the duration as well as the time to event will be displayed in months and a final decision will be made at the last BRPM.

Tabulations of frequencies for categorical data will include all possible categories and will display the number of observations in a category as well as the percentage (%) relative to the respective treatment group (unless otherwise specified, all patients in the respective patient set whether they have non-missing values or not). Percentages will be rounded to one decimal place. The category missing will be displayed only if there are actually missing values. The denominator of the main categories is defined by the number of patients in the used patient set. The main categories define the denominators of the subcategories. Subcategories should be intended and "[N(%)]" will be displayed only for the main category. If a table includes only categorical data, "[N(%)]" is to be displayed in the column header.

If applicable, conversion from days to weeks, months and years will be as follows:

- Weeks = Days/7
- Months = $(Days \times 12)/365.25$
- Years = Days/365.25

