For Uric Acid and Hypokalemia, the CTCAE grade cannot always be assigned by the laboratory parameter itself as two different CTCAE grades have the same laboratory constellation, but are distinguished by additional clinical parameter. In this case a CTCAE grade of -1 will be assigned initially. Patients with a CTCAE grade of -1 will be treated as

- Grade 1 for Uric Acid
- Grade 1 for Hypokalemia

for all analyses. In laboratory listings, the CTCAE grade will be displayed as -1.

Patients with hepatic enzyme elevation will be tabulated. With respect to neutropenia, thrombocytopenia and leukopenia episodes the number of episodes and mean and median duration will be displayed. Additionally, laboratory values of special interest as described in Section 5.4.5 will be analyzed.

Additionally, a frequency table displaying number of patients with episodes of grade 4 neutropenia and concomitant AEs in the user-defined AE category (UDAEC) of any grade and grade 3/4 will be provided. In this context, concomitant AE is defined as AE with onset date within the neutropenia episode. The same table will be done for grade 3/4 episodes of neutropenia and concomitant AEs in the UDAEC of any grade and grade 3/4 will be done. The same applies for the display of patients with thrombocytopenia and bleeding events. For the definitions of neutropenia, thrombocytopenia and leukopenia episodes please refer to Section 5.2.5.2.

The prioritized laboratory values (see Section 5.4.5) will be displayed in Section 15 of the final CTR while all other laboratory parameters will be displayed in the Appendix of the CTR.

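### Recorded cytopenia durations depend on the visit grid, whose 7-day gap equals the SAP's 7-day cut, and sampling changed with protocol version 6, yet the SAP neither bounds nor splits the durations

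*SAP*

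**What the plan says.** SAP 5.4.5.2 singles out episodes of low neutrophils, platelets and white cells. Taking neutrophils as its example, it opens an episode at the first recorded grade 3 or higher and closes it at the first recorded grade 2 or lower. It adds a threshold: "CTCAE grade 4 lasting 7 or more days will be analyzed". If an episode starts at the EOT visit or in follow-up, its duration is set to missing, because sparse sampling there would make it look too long.

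SAP 7.8.2 gives the output: "With respect to neutropenia, thrombocytopenia and leukopenia episodes the number of episodes and mean and median duration will be displayed". SAP 7 gives the layout: "Displays of safety data will be presented by dose cohort and in total". Neither section separates durations by protocol version.

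On sampling, Protocol 5.2.3.1 now reads: "Blood samples should be collected more frequently in case of relevant toxicities; e.g. in case of grade 4 neutropenia or thrombocytopenia". It states no interval. Protocol section 11 shows that modification 5, dated 04 March 2015, added this sentence. The stated reason begins "Change 5: More frequent measurements in case of relevant findings" and goes on to name the duration of grade 4 neutropenia and thrombocytopenia. SAP 5.1 identifies the version when it describes the DLT change made at the same time: "With CTP version 6 (04 March 2015), the following additional haematologic AEs were considered DLT".

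**The concern.** A duration read from first qualifying sample to first clear sample measures the spacing of visits as well as the illness. Here the widest scheduled gap coincides with the SAP's cut of 7 days, so the count of prolonged grade 4 episodes rests on the point where the grid does most to determine the answer.

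The sampling advice changed during the trial, and its stated purpose was to measure these durations better. Episodes from the two periods then enter the same mean, median and 7-day count. The SAP is alert to the problem elsewhere: it blanks durations after EOT for this reason, and for DLTs it applies the protocol version in force. It has neither safeguard for on-treatment episodes.

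These tables matter because Protocol 5.2.1.1 says haematological events will be weighed when the dose for further development is defined. Recorded length also feeds a second table in SAP 7.8.2, where an adverse event counts as concomitant if it starts within the neutropenia episode. A stretched episode captures more of them.

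**Working it through.** The documents give no duration figure to reproduce, so the check places a true episode on the scheduled visits.

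**Inputs**
- Safety laboratory days: 1, 2, 3, 4 and 8 in course 1; 1, 2, 3 and 8 in later courses (Protocol flow charts and 6.2.2).
- Course length 14 days, so the next visit after day 8 is day 15, followed by days 16, 17 and 22 if the course starts on time.
- Recorded duration = day of first clear sample − day of first qualifying sample. The SAP gives no formula; a date difference is assumed. Counted inclusively, each reading is one day longer.
- Assumptions: onset uniform over the course, no unscheduled samples, courses on time. The day 3 window in later courses is not varied.

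**True 4-day episode, nominal day 8**

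| Onset (day) | First seen | First clear | Recorded | Days of onset |
|---|---|---|---|---|
| 1–2 | 2 | 8 | 6 | 1 |
| 2–3 | 3 | 8 | 5 | 1 |
| 3–4 | 4 (course 1 only) | 8 | 4 | 1 |
| 4–8 | 8 | 15 | 7 | 4 |
| 8–11 | missed | – | – | 3 |
| 11–12 | 15 | 16 | 1 | 1 |
| 12–13 | 15 | 17 | 2 | 1 |
| 13–15 | 15 | 22 | 7 | 2 |

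- Detected onset days: 11 of 14 in course 1, 10 of 14 in each later course. Over four courses: 11 + 3×10 = 41.
- Recorded as 7 or more: 4 + 2 = 6 per course, so 24/41 = **59%**. All of these read exactly 7; none exceeds 7. The median is 7.
- Mean recorded: course 1 sums to 6+5+4+28+1+2+14 = 60, each later course to 56. (60 + 3×56)/41 = 228/41 = 5.6 days, against a true 4.

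**Day 8 visit moved within its +2 window**
- Day 9: onset on days 1–2 reads 7 and on days 13–15 reads 8, giving 3 per course: 12/41 = **29%**. Mean (61 + 3×56)/41 = 5.6.
- Day 10: onset on days 1–2 reads 8, on days 2–3 reads 7 and on days 13–15 reads 9, giving 4 per course: 16/41 = **39%**. Mean (62 + 3×56)/41 = 5.6.

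The window lowers the 7-day count but leaves the upward shift in the mean.

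**Next course delayed.** Visits are then at least weekly (Protocol 5.2.3.1), so days 16 and 17 drop out and onset on days 11–15 reads 7. In course 1: (4 + 4)/11 = 73%, against 6/11 = 55% on time.

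**After version 6.** The interval is not stated. With a sample every 2 to 6 days after detection, a 4-day episode reads at most 6 days, so 0% reach 7. Weekly extra samples would still allow 7. With a 3-day interval, simulation of course 1 gives a mean of 3.8 days, against 5.4 on the scheduled grid.

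**The error also runs the other way.** A true 8-day episode starting between days 4 and 8 reads 7 if it ends by day 15, which is 3 of the 4 onset days (75%).

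**What simple bounds would do on the nominal grid**
- Minimum duration (first to last qualifying value) reaches 7 for 2 of 14 onset days of a true 8-day episode (14%) and 6 of 14 of a true 10-day episode (43%).
- Maximum duration (last clear value before to first clear value after) reaches 7 for 9 of 11 detected onset days of a true 4-day episode in course 1 and 9 of 10 later: 36/41 = 88%.

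**The case against.** The strongest reply is that this is a descriptive laboratory table and that the contrast between periods is assumed on both sides. Much of that stands.

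- The sampling sentence is advice, not a requirement. It names only grade 4 neutropenia and thrombocytopenia, as examples; leukopenia and grade 3 episodes are not mentioned. Unscheduled samples may also have been taken earlier.
- The earlier grid was not constant. Modification 3 (August 2012) replaced the flow chart. Modification 4 (August 2013) added the +2 window to day 8. Modification 5 removed it for course 1 only. Where the window was used, 59% is the wrong figure and 29–39% is nearer.
- The on-time grid does not fit persistent grade 4 counts, because Protocol 4.1.4 holds the next course for low counts. That is right, but weekly visits then make the reading longer, not shorter.
- Requiring the minimum duration to reach 7 days would undercount truly prolonged cytopenia. This is correct and shapes the fix.

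A reader might infer that every short early episode is turned into one of 7 days. The documents do not support that: many read 1 to 6 days and some are missed. A reader might also infer that the change hides or reverses a dose relation. Escalation is sequential, so period and dose may well align, but no passage dates any cohort, and SAP 7.8.1.2 plans no formal safety comparison.

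**Conclusion.** The concern holds as a measurement and reporting defect. Followed as written, the SAP produces on-treatment durations that the visit grid pushes upward for short episodes, and it combines periods with different sampling advice without saying so. For a true 4-day episode the scheduled grid gives a mean of about 5.6 days and a 7-day reading in about 59% of detected cases on nominal day 8, or 29–39% with day 8 moved to day 9 or 10. These figures assume uniform onset, courses on time and no extra samples; the size of the difference from version 6 onward depends on an interval the protocol does not give.

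The point does not reach the primary endpoint. Before version 6 these haematological DLT criteria did not apply. From version 6 the duration criterion is more than 7 days, which a reading of exactly 7 does not meet, and DLTs are qualifying adverse events, not the SAP's derived laboratory episodes. Any distortion of the dose pattern is a possibility that cannot be sized from the documents.

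**What to change.** In SAP 5.4.5.2 and 7.8.2:

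1. Keep the planned duration and state its formula.
2. For each episode add a minimum duration (first to last qualifying value) and a maximum duration (last non-qualifying value before to first non-qualifying value after). An episode seen only on day 8 of course 1, clear on days 4 and 15, would show 0 and 11 days beside the planned 7.
3. Report the count of 7 days or more under both bounds side by side, with neither as the main count.
4. Show the duration tables also split by whether the episode started before or from protocol version 6, and say in a footnote that the sampling advice changed.

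Interval-censored modelling is optional; in cohorts this small it is not needed.

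The cost is SAP wording and a little programming on dates already collected. The downside is wider ranges for episodes on the sparse grid, which is what those data can support.
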